1. BACKGROUND

Patients diagnosed with myeloproliferative neoplasms (MPNs)—including primary myelofibrosis (MF), essential thrombocythemia (ET), and polycythemia vera (PV)—face progressive bone marrow diseases largely driven by JAK2, CALR, or MPL mutations.¹⁻⁴ These conditions lead to overproduction of mature blood elements, marrow fibrosis, and heightened risks of thrombosis, cardiovascular events, and inflammatory complications.⁵⁻⁷ Although some patients live decades post-diagnosis, quality of life is often significantly reduced, and transformation to acute leukemia (MPN-BP) carries poor outcomes.⁸⁻⁹

Despite affecting an estimated 300,000 individuals in the U.S.,¹⁰ much remains unknown about the biological drivers of disease progression, predictive biomarkers, and meaningful surrogate endpoints. Existing MPN registries have provided valuable but limited insights, often constrained to single-center, clinician-reported, or trial-based cohorts.¹¹ This Registry addresses these gaps by integrating electronic medical records (EMRs), patient-reported outcomes (PROs), claims data, and genomic profiles across a broad patient spectrum—including pre-fibrotic MF (pre-PMF), MPN-AP, MPN-BP, or post-MPN AML, and MDS/MPN overlap syndrome (defined as CMML, MDS/MPN-SF3B1-T, MDS/MPN with neutrophilia, or MDS/MPN not otherwise specified), including patients originally diagnosed with one of these conditions but who have received one or more SCTs and/or BMTs—supporting comprehensive longitudinal tracking of disease evolution, treatment response, and EMR.

1.1 Study Rationale

Historically, efforts to understand MPN disease progression have been siloed within individual research centers, leaving critical data gaps despite decades of published studies and a few approved therapies. This Registry aims to establish a robust, longitudinal observational research platform to address these unmet needs, benefiting the broader MPN community.

Using a digital health platform, the Registry will collect multimodal data—centered on patient (EMRs) and enriched by self-reported outcomes. The cohort will include patients diagnosed with primary or secondary MF, ET, PV, pre-PMF, MPN-unclassifiable (MPN-U), MPN-AP, and MPN-BP or post-MPN AML, MDS/MPN overlap syndrome as defined above. This will also include patients originally diagnosed with one of these conditions but who have received one or more SCTs and/or BMTs.

By integrating EMR data, PROs, claims data, and linked registries, this study enables comprehensive longitudinal analysis of disease trajectories, treatment patterns, and quality-of-life outcomes. The Registry's real-world evidence (RWE) will help identify early predictors of progression, validate surrogate endpoints, and support future clinical trials and drug development.

Ultimately, this infrastructure will enhance regulatory decision-making, inform treatment guidelines, and improve prognostic modeling—advancing precision care and outcomes for patients with MPNs.

2. PURPOSE

The purposes of the MPN PROGRESSION Registry™ (“Registry”) are to:

- **Facilitate high-quality observational research** by collecting and analyzing EMRs, PROs, and linked external datasets — including mortality records, insurance claims, genetic testing results, and affiliated registries — to advance understanding of disease natural history, progression, real-world therapeutic effectiveness, and standards of care.
- **Improve clinical definitions of MPN disease progression** by incorporating updated diagnostic criteria and emerging biomarkers, ensuring refined characterization of pre-fibrotic myelofibrosis (pre-PMF), MPN in accelerated phase (MPN-AP), MPN in blast phase (MPN-BP) or post-MPN AML, and MDS/MPN overlap syndrome as defined above
- **Identify predictive biomarkers and surrogate endpoints** to support drug development, regulatory decision-making, and improved understanding of disease progression.
- **Enhance standards of care and patient outcomes** by leveraging RWE and longitudinal analytics to inform treatment sequencing, monitor therapeutic responses, and guide personalized care strategies.
- **Support participant identification for future research** by enabling review of Registry data to identify and contact individuals eligible for future studies conducted by the MPN Research Foundation or approved collaborators.

3. OVERALL STUDY DESIGN

This is a prospective, non-interventional observational study, designed to evaluate patients with MPNs using both historical and prospective data. Participants will be enrolled over a minimum of three years during the initial run-in phase and followed longitudinally for disease progression, treatment response, clinical outcomes, and survival until withdrawal from the registry or death. Some participants may be followed for over ten years.

The study uses a multimodal data collection strategy, integrating:

- **EMRs:** Structured data extractions, including laboratory results, imaging, clinical notes, and treatment history.
- **PROs:** Longitudinal assessments of symptoms, quality of life, and functional status.
- **Medical Claims and Insurance Data:** Real-world healthcare utilization, treatment adherence, and cost metrics.
- **Mortality Data:** Vital status and cause-specific mortality obtained through national mortality dataset linkages, ensuring accurate survival analyses and minimizing loss to follow-up.
- **Affiliated Registries:** Select collaborations (e.g., CIBMTR, NCDB, SEER) may be used for external validation and cross-registry comparisons, though integration with international registries such as the European LeukemiaNet (ELN) will be considered only after addressing jurisdictional and data governance factors.

In addition to evaluating disease and treatment outcomes, the Registry will systematically monitor enrollment feasibility, participant retention, and heterogeneity across demographic, clinical, and geographic dimensions. These metrics will support reporting obligations to federal registries (e.g., ClinicalTrials.gov) and inform future feasibility assessments for interventional trials.

4. OBJECTIVES

4.1. Primary Objectives

Stage 1: Feasibility Phase

The study will begin with a 12- to 24-month feasibility phase focused on participant retention, data completeness, EMR integration, and engagement strategies. Results from this phase will help optimize study operations, guide participant engagement, and inform potential protocol amendments.

- Evaluate enrollment feasibility and participant characteristics during the first 12–24 months.
- Characterize participant demographics, geographic distribution, and clinical settings.
- Assess inclusion of underrepresented populations to enhance the generalizability and heterogeneity of RWD.
- Assess representativeness of enrolled participants relative to the broader U.S. MPN population, ensuring alignment with clinical and demographic patterns.
- Determine the proportion of participants providing a Minimal Viable Dataset (MVD) at enrollment.
- Monitor consent rates for longitudinal EMR access and secondary data use.
- Identify gaps in baseline data completeness and develop strategies to mitigate missing information.
- Track participant retention at 12, 18, 24, and 36 months, and evaluate completion of at least three consecutive follow-ups.
- Identify early indicators of dropout or disengagement to inform retention strategies.
- Monitor response rates to quarterly PRO surveys (e.g., MPN-SAF TSS, PROMIS Short Form v1.0 – Fatigue 8a) and evaluate follow-up strategies (automated vs. manual).
- Assess the proportion of participants using secondary contacts (caregivers, clinicians) for follow-up.
- Measure success rates of EMR integration across sites using FHIR-based interoperability, compare self-reported and EMR-extracted data, and validate processing scalability.

Stage 2: Surrogate Endpoint Phase

- Establish composite surrogate endpoints integrating genetic markers (e.g., variant allele frequency shifts), clinical indicators (e.g., fibrosis progression, cytopenias), inflammatory markers (e.g., cytokine levels), and PROs (e.g., MPN-SAF TSS, PROMIS trends).
- Ensure surrogate endpoints align with FDA and EMA regulatory standards for clinical trials.
- Incorporate RWD (EMR, claims, PROs) to validate surrogate markers of disease progression.
- Determine time from baseline to first progression event (e.g., ET → PV → MF, blast phase transformation) and assess median time to progression by subtype.
- Measure progression rates per WHO 2022/IWG-MRT criteria using updated risk stratification models.
- Develop surrogate endpoints predictive of disease progression and treatment response to support drug development.
- Compare progression rates in treated vs. untreated cohorts and validate endpoints using external registries (e.g., SEER, NCDB, Mayo Clinic MPN Database, ELN).
- Monitor overall survival (OS) and progression-free survival (PFS), evaluating prognostic significance of surrogate endpoints for future trials.

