5. PARTICIPATION CRITERIA

5.1 Inclusion Criteria

- Confirmed diagnosis of pre-PMF, primary MF, secondary MF, PV, ET, MPN-U, MPN-AP, MPN-BP or post-MPN AML, and MDS/MPN overlap syndrome as defined above per WHO 2022 criteria, including patients originally diagnosed with one of these conditions but who have received one or more SCTs and/or BMTs
- Willingness and ability to provide written informed consent.

- Willingness and ability to complete patient assessments, independently or with minimal assistance.
- Accessible EMR data from a participating healthcare institution to enable longitudinal data collection.
- U.S. residency, where the Registry has regulatory approvals and data-sharing agreements.
- Reasonable expectation of ongoing medical care and follow-up data availability for longitudinal objectives.

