5.2 Exclusion criteria

Participants will be excluded if they meet any of the following:

1. Lack of EMR data access due to technical limitations, non-participating institutions, or missing patient authorization (self-reported or claims-only data is insufficient for inclusion).
2. Missing compulsory data elements: WHO 2022 MPN diagnosis, date of initial diagnosis, or baseline demographics.
3. Lack of capacity to provide informed consent and absence of a legally authorized representative.
4. Significant gaps in clinical history, lab data, treatment records, or follow-up availability that limit longitudinal analysis.
5. Revised diagnosis to a non-MPN hematologic malignancy or other condition outside WHO 2022 criteria (other than post-MPN AML, and MDS/MPN overlap syndrome as defined above); such participants will be removed from future analyses.
6. Enrollment in external studies that restrict medical data access or impose data-sharing limitations incompatible with this Registry.

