9.6 Missing Data and Sensitivity Analyses

Patients or their legal representatives lost to follow-up will be contacted via phone or electronically (e.g., email). Missing data will be clearly identified and handled in line with the principles detailed in the SAP. While primary analyses will rely on complete-case data, sensitivity analyses will evaluate the impact of missing data assumptions using multiple imputation methods³⁰ and other appropriate strategies to ensure robustness of study findings. Additional sensitivity analyses will include assessments of the robustness of results across varying assumptions for distributional assumptions, model specifications, and subgroup effects. Patients not meeting the minimum data requirements will be excluded from analyses.

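### Several Stage 1 feasibility measures are taken in people already selected on the same properties: uninformative for items that entry requires, biased upward for the rest

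*Protocol*

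**What the plan says.** Section 4.1 lists these among the primary objectives of the 12- to 24-month feasibility stage:

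- On the minimum dataset, the objective reads "Determine the proportion of participants providing a Minimal Viable Dataset (MVD) at enrollment".
- On technical linkage of records, it reads "Measure success rates of EMR integration across sites using FHIR-based interoperability".
- On missing items at entry, it reads "Identify gaps in baseline data completeness and develop strategies to mitigate missing information".
- On permissions given by the participant, it reads "Monitor consent rates for longitudinal EMR access and secondary data use".

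The same section says that the results will guide operations and possible amendments.

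Eligibility selects on the same properties. Section 5.1 requires "Accessible EMR data from a participating healthcare institution to enable longitudinal data collection". Section 5.2 excludes on three related grounds:

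- Exclusion 1: "Lack of EMR data access due to technical limitations, non-participating institutions, or missing patient authorization".
- Exclusion 2: a missing diagnosis, diagnosis date or baseline demographics.
- Exclusion 4: "Significant gaps in clinical history, lab data, treatment records, or follow-up availability that limit longitudinal analysis".

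Section 9.6 applies a further filter at analysis: "Patients not meeting the minimum data requirements will be excluded from analyses". It makes no exception for Stage 1.

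No Stage 1 measure is given a denominator of people screened or people consented.

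**The concern.** A feasibility proportion is informative only if the failures stay in its denominator. Here the rules that decide who counts as an eligible, analysable participant are largely the same as the properties being measured. Someone who signs consent and then cannot be linked is the failure that Stage 1 should detect. Under exclusion 1 that person is an exclusion, and nothing says they also count as a failed integration.

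The stake is the use made of Stage 1. If linkage or completeness problems are removed before counting, the results cannot show whether EMR linkage and baseline data capture work, and amendments would rest on figures that are too favourable. If consented-then-removed people are not logged from the start, the count may be impossible to recover.

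**Working it through.** The protocol states no target, threshold or expected rate for any of these measures, so there is no figure to reproduce. The check has two parts.

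**1. Can failures arise after consent and then be removed?**

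- The pre-consent portal questions on records and EMR access (Section 10.6, Q9 and Q10) are answered by self-report.
- The portal accepts an unsure diagnosis date without disqualifying the person (Section 10.6), while exclusion 2 excludes for a missing date.
- Consent is the step that permits record access (Section 6.2). The portal confirms enrollment once consent is complete (Section 10.7). The initial EMR extraction belongs to the baseline timepoint (Section 6.3.1).
- Section 5.2 can act after entry: its exclusion 5 removes people from later analyses when the diagnosis is revised.

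A linkage failure or a missing compulsory element can therefore surface after consent, and 5.2 then removes the person. No section keeps that person in the Stage 1 count.

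**2. How much does removal change the proportion?**

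Let f be the fraction of consenting people removed under 5.2(1), (2) or (4). Let q be the share of those remaining who also have any MVD items beyond the entry elements. Both are assumptions. An MVD is taken to need at least the entry elements.

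- Reported among those remaining: q
- Among all who consent: (1 − f) × q
- Ratio of reported to consented-population value: 1/(1 − f), which is 1.11, 1.33 or 1.67 for f = 10%, 25% or 40%

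*Case A: the MVD contains only entry elements (q = 1).* The reported value is 100% whatever f is. The value among consenters is 1 − f, that is 90%, 75% or 60%. The same algebra applies to baseline EMR access, authorization and the compulsory elements.

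*Case B: the MVD needs further items.* Section 6.3.1 also collects baseline PROs, claims and molecular results where available, and the entry criteria do not require these to be complete.

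| Reported (q) | Consenters, f = 10% | f = 25% | f = 40% |
|---|---|---|---|
| 90% | 0.90 × 0.90 = 81% | 0.75 × 0.90 = 67.5% | 0.60 × 0.90 = 54% |
| 70% | 0.90 × 0.70 = 63% | 0.75 × 0.70 = 52.5% | 0.60 × 0.70 = 42% |
| 50% | 0.90 × 0.50 = 45% | 0.75 × 0.50 = 37.5% | 0.60 × 0.50 = 30% |

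The measure is inflated but can still vary.

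*Case C: the Section 9.6 exclusion is applied and its minimum requirement is the MVD.* Everyone left has an MVD, so the result is 100% for any q.

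*Contrast.* If 5% to 20% of those who self-report EMR access fail verification and stay in the denominator, EMR access reads 95% to 80%. The choice of denominator decides whether the problem is visible.

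**The case against.** The strongest reply is that the protocol's enrolled population is already the consented one. The portal confirms enrollment at consent, extraction follows, and Section 5.2 itself speaks of participants being excluded. On that reading an unlinkable person is in the denominator. Section 9.6 can also be read as governing the progression and survival analyses of Section 9.1. Data completeness is reported by other routes as well: the annual interim reviews (9.2), milestone monitoring and the vendor's quarterly reports (9.9). The MVD definition and metric denominators may sit in the SAP, and their absence from the protocol is not held against it here.

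Much of this stands as a limit on the point. A reader might infer that all the Stage 1 measures come out near 100% by construction. The documents do not support that:

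- The MVD is not defined, so it may include items that entry does not require.
- Only significant gaps exclude, so lesser gaps and missing PRO, claims or molecular data remain visible.
- Integration is to be measured across sites, and the same objective includes agreement of self-reported with EMR data and processing scalability. Eligibility fixes neither.
- Consent to secondary use, the six-monthly renewal of EMR permission (6.3.2), PRO response and retention are all free to vary.

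The reply does not remove the core. Treating consent as enrollment does not say what happens to the count once exclusion 1, 2 or 4 is applied, and 9.6 is worded without limit. The conflict lies between objectives, eligibility and an analysis exclusion that the protocol itself fixes. A SAP that followed 5.2 and 9.6 as written would be led to the selected denominator.

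**Conclusion.** The point holds in a limited form. Baseline EMR access and authorization, and the compulsory elements, are 100% by definition among people who satisfy entry and carry no feasibility information. The MVD proportion, integration success and baseline completeness are biased upward. For the MVD the inflation factor is 1/(1 − f), with f not given in the protocol. The MVD is forced to 100% only if it holds nothing beyond the entry elements, or if the 9.6 exclusion is applied to it.

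This rests on 5.2 and 9.6 being applied as written before Stage 1 is counted. The rates of 10%, 25% and 40% are illustrative. The weight is moderate: these are primary objectives meant to steer amendments, but no go/no-go threshold depends on them.

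**What to change.** - **Section 4.1:** state that the denominator for the MVD proportion, initial EMR access and authorization, EMR integration success (where counted per person) and baseline completeness is everyone who completes the ICF, the point at which the portal confirms enrollment. Count people later removed under 5.2(1), (2) or (4) as failures, with the reason.
- **Section 5.2:** state that removals after consent are logged and kept in the Stage 1 counts.
- **Section 9.6:** state that the minimum-data exclusion applies to the outcome analyses and not to the Stage 1 feasibility metrics.
- **Reporting:** give the number stopped at pre-screen Q9 and Q10 alongside, as far as the permission described in Section 10.6 allows.

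The eligibility criteria themselves need not change. The cost is wording in three sections and a log of consented-then-removed people, with no new participants or data collection. The feasibility percentages will look less favourable.

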4.2. Secondary Objectives

- **Characterize Disease Burden and Risk Stratification**
Develop a composite risk model distinguishing high- and low-risk patients by integrating genetic, inflammatory, and clinical markers. Assess how cytokine levels and inflammatory pathways influence disease trajectory and symptom burden.
- **Evaluate Treatment Response as a Surrogate for Disease Progression**
Compare progression rates in patients treated with JAK inhibitors, interferons, investigational agents, and other drugs. Determine whether therapy-induced molecular or clinical changes correlate with improved outcomes.
- **Analyze Genetic and Morphological Disease Evolution**
Monitor available variant allele frequency (VAF) changes in high-risk mutations and evaluate bone marrow fibrosis progression, where data is available, to understand clinical implications.
- **Assess Quality of Life and Symptom Burden at Disease Progression**
Track longitudinal changes using validated PROs, including MPN-SAF TSS, EORTC QLQ-C30, modified PHQ-9, PGI-S, and PROMIS Short Form v1.0 – Fatigue 8a, to evaluate how symptom burden correlates with disease progression

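### Stage 2 sets out to establish and validate surrogate endpoints, but a non-interventional registry with only observational validation sources can identify candidate surrogates and cannot show that they carry a treatment effect

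*Protocol*

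**What the plan says.** **The aim.** The first Stage 2 bullet of Protocol 4.1 is to establish composite surrogate endpoints from genetic, clinical, inflammatory and patient-reported components. The next two are to "Ensure surrogate endpoints align with FDA and EMA regulatory standards for clinical trials" and to "Incorporate RWD (EMR, claims, PROs) to validate surrogate markers of disease progression". Later bullets are to "Develop surrogate endpoints predictive of disease progression and treatment response to support drug development", and to compare treated with untreated cohorts and validate endpoints in external registries. Section 1.1 expects the registry's evidence to help "validate surrogate endpoints, and support future clinical trials and drug development". Section 2 uses a milder verb: it speaks of identifying biomarkers and surrogate endpoints, "to support drug development, regulatory decision-making, and improved understanding of disease progression".

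**The design.** Section 3 states: "This is a prospective, non-interventional observational study, designed to evaluate patients with MPNs using both historical and prospective data". Section 7.1 adds that the study is not a clinical trial.

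**The evidence.** The last Stage 2 bullet concerns overall and progression-free survival, "evaluating prognostic significance of surrogate endpoints for future trials". Section 4.2 compares progression between drug classes and asks to "Determine whether therapy-induced molecular or clinical changes correlate with improved outcomes". Section 9.7 plans propensity scores for comparisons between treatment groups. Table 1 in section 9 gives power for the association of a risk marker with progression.

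**The concern.** A prognostic marker and a surrogate endpoint answer different questions. A marker is prognostic if patients with worse values do worse. It can replace the outcome in a trial only if the effect of treatment on the marker predicts the effect of treatment on the outcome. That requires credible treatment effects on both, normally from randomised comparisons. A marker can be strongly prognostic, and be confirmed as such in every other registry, without meeting this requirement.

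Sections 1.1 and 4.1 tie the surrogates to future trials, treatment response and drug development, so the second question is the relevant one. If the plan is followed as written, Stage 2 could call a marker validated on evidence that addresses only the first question, supplemented by confounded treatment contrasts. A later trial relying on that label could credit a drug with benefit because it moves the marker.

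**Working it through.** **1. Claim against evidence**

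| Evidence planned | Where | What it can show |
|---|---|---|
| Prognostic significance for survival outcomes | 4.1, Stage 2 | Patient-level association of marker and outcome |
| Correlation of on-treatment change with outcome | 4.2 | Association within treated patients; responders may differ in prognosis for other reasons |
| Treated versus untreated; between drug classes | 4.1, 4.2, with 9.7 | A treatment contrast adjusted for measured covariates only |
| External validation or comparison: CIBMTR, NCDB, SEER, a Mayo Clinic database, ELN and other European registries, claims-based registries | 3, 4.1, 4.3 | Whether an observational association replicates |

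No row supplies a randomised treatment effect on marker and outcome, and no randomised data source is named.

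**2. What the power statement covers**

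Inputs from section 9: power 80%, type 1 error 5% (sidedness not stated; two-sided fits), progression in 50%. For a binary marker of prevalence p, the Schoenfeld formula gives

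HR = exp[(1.960 + 0.842) / √(N × 0.5 × p(1 − p))].

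- N = 1000, p = 10%: √45 = 6.708; 2.802 / 6.708 = 0.418; HR = 1.52. Table 1 prints 1.53.
- N = 2000, p = 20%: √160 = 12.65; 2.802 / 12.65 = 0.221; HR = 1.25. Table 1 prints 1.25.

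All 16 cells agree within 0.015. At the planned enrolment of about 1500, which has no row in the table, the same formula gives 1.41, 1.29, 1.25 and 1.23 for prevalences of 10, 20, 30 and 50%. Table 1 is therefore sound for its purpose, but that purpose is power for a prognostic association. It says nothing about surrogacy.

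**3. Illustration only**

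All inputs here are assumed and none comes from the protocol. There are 200,000 simulated patients. Unmeasured severity U is standard normal. The marker is U − 0.5 × treatment + noise (SD 0.7). The hazard is proportional to exp(0.7 U), so treatment has no true effect on outcome. Half the patients have the event. The log-odds of being treated are c × U. Hazard ratios are from Poisson rate models.

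| Allocation | Marker HR per unit | Marker difference, treated − untreated | Treatment HR | Treatment HR adjusted for marker |
|---|---|---|---|---|
| Randomised | 1.54 | −0.50 | 1.00 | 1.26 |
| Healthier treated, c = −0.8 | 1.53 | −1.19 | 0.65 | 1.06 |
| Healthier treated, c = −0.4 | 1.54 | −0.90 | 0.79 | 1.16 |
| Sicker treated, c = 0.4 | 1.54 | −0.12 | 1.26 | 1.35 |
| Sicker treated, c = 0.8 | 1.55 | 0.20 | 1.54 | 1.45 |

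In the randomised row, the prognostic HR with a 0.50-unit reduction would predict exp(−0.50 × ln 1.54) = 0.81, while the actual treatment HR is 1.00. The marker HR is almost the same in every row, so it cannot separate these situations. In the second row a treatment with no effect appears to improve both marker and outcome, and adjusting for the marker moves the treatment HR from 0.65 to 1.06. That pattern could be mistaken for evidence of surrogacy.

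**The case against.** - **Regulatory standard.** A reader might infer that the protocol promises validation to FDA and EMA standard. No sentence says so. One bullet says surrogates should align with those standards and a separate bullet says validate. The documents also do not state what either agency requires. The point does not depend on that inference.
- **Softer wording elsewhere.** Section 1.1 says the evidence will help to validate, and section 2 says identify. The 4.1 bullet on prognostic significance and the 4.2 bullet on correlation describe the evidence accurately. This stands: those two bullets are not errors. They show how far the evidence falls short of the verbs *establish* and *validate* in the other Stage 2 bullets.
- **Not purely prognostic.** A reader might infer that the plan contains nothing but marker-outcome association. It also has comparisons between treatments, with propensity scores (9.7) and time-dependent covariates (9.5). A drug that lowered the marker without lowering progression could show up there. This stands in part: such comparisons are informative, but they balance measured covariates only.
- **Left to the SAP.** Methods may properly be left to the SAP. No method, however, supplies randomised treatment effects that the named sources do not contain. Section 5.2 excludes only participants in external studies that restrict data access, so some participants may be in randomised trials, but nothing plans to obtain or use their allocation.
- **The simulation.** Its result follows from its assumptions, including the null treatment effect. It should not be read as an estimate of bias in this registry.
- **Remote harm.** The registry assigns no treatment, and harm would need a later trial to rely on the label. That is fair, and it limits the point to the objectives and what may be concluded from them.

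**Conclusion.** The point holds in this form: the Stage 2 objectives and the rationale claim more than the design can deliver. The registry can show that a marker is prognostic, that the association replicates in other registries, and that the marker is a reasonable candidate surrogate. It cannot show that a treatment effect on the marker reliably predicts a treatment effect on outcome.

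No stated figure is wrong and Table 1 reproduces. What is affected is the conclusion Stage 2 is entitled to draw under a primary objective. The verdict rests on two readings of the protocol: that the surrogates are meant for use in trials of treatment (1.1, 2 and 4.1), and that the named sources are all observational (3, 4.1, 4.3 and 7.1). It does not rest on the simulated hazard ratios or on any particular regulatory requirement.

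**What to change.** 1. In 1.1 and the Stage 2 bullets of 4.1, replace establishing or validating surrogate endpoints with *identify and prognostically evaluate candidate surrogate endpoints (patient-level association, replicated in external registries)*. Apply the same limit to the bullet on treatment response and drug development. This matches the verb already used in section 2.
2. State in 4.1 that validating a surrogate for treatment effect needs randomised-trial data. Either name such a source or say that this step lies outside the registry.
3. In 4.2, keep the treatment comparisons and the on-treatment correlation, but describe them as supportive evidence that is prone to confounding.
4. In 9.9, add confounding by indication to the listed biases. Section 9.7 already acknowledges confounding, but the list in 9.9 names misclassification, recall bias and missing data.

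The cost is a less ambitious stated claim. Data collection and analyses are unchanged.
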